## Brief Summary

This observational study aims to examine the association between Q-angle and plantar loading characteristics in physically active young adults. Q-angle is a commonly used clinical measure of lower-extremity alignment, but its relationship with regional plantar loading during gait remains unclear. Participants will undergo bilateral Q-angle assessment and plantar pressure evaluation during walking. The study will investigate whether Q-angle is associated with specific plantar loading variables across different foot regions in active young adults.

## Detailed Description

This observational study is designed to investigate the association between Q-angle and plantar loading characteristics in physically active young adults. Q-angle is a commonly used measure of lower-extremity alignment, but its relationship with regional plantar loading during gait has not been fully clarified.

Participants will undergo bilateral Q-angle assessment under standardized conditions and dynamic pedobarographic evaluation during walking. Plantar pressure variables will be obtained for different foot regions, including the toes, forefoot, midfoot, hindfoot, and total foot. The primary objective is to determine whether Q-angle is associated with selected regional plantar loading variables. Secondary analyses will explore whether these associations differ according to sex and limb dominance.

Statistical analyses will be performed using linear mixed-effects models to account for within-subject dependence between bilateral measurements. This study focuses on the relationship between lower-extremity alignment and regional plantar loading patterns in physically active young adults.

## Study Design

- **Study Type:** Observational
- **Observational Model:** Other
- **Time Perspective:** Cross-Sectional

- **Enrollment:** 92 participants
- **Enrollment Type:** Actual
- **Number of Groups/Cohorts:** 1

## **Study Population**

Physically active young adults aged 18 years and older who are able to walk independently and who have no current lower-extremity injury, previous lower-extremity surgery, neurological disorder, vestibular disorder, structural deformity, or musculoskeletal pain affecting gait or balance.

## **Sampling Method**

**Non-Probability Sample**

## **Group/Cohort**

**Group/Cohort Label**

**Physically active young adults**

**Group/Cohort Description**

Physically active young adults who underwent Q-angle measurement and plantar pressure assessment during walking. No therapeutic or preventive intervention was applied.

## **Intervention / Exposure**

**Intervention Name**

**Q-angle and plantar pressure assessment**

**Intervention Description**

Participants underwent observational Q-angle measurement and dynamic plantar pressure assessment during walking. No therapeutic or preventive intervention was administered.

## **Eligibility Criteria**

**Inclusion Criteria**

1. Age 18 to 27 years
2. High physical activity level according to the International Physical Activity Questionnaire-Short Form (IPAQ-SF) classification
3. Ability to complete the assessment procedures independently
4. Voluntary agreement to participate

## **Exclusion Criteria**

1. History of lower-extremity injury within the previous 6 months
2. Previous lower-extremity fracture or surgery
3. Known neurological or vestibular disorder affecting gait or balance
4. Current musculoskeletal pain in the spine or lower extremities during assessment
5. Diagnosed structural lower-extremity deformity
6. Inability to complete the assessment procedures independently

## **Outcome Measures**

### **Primary Outcome Measure**

#### **Association between Q-angle and regional pedobarography outcomes**

**Description:** Regional plantar pressure, force, contact area, and contact time outcomes assessed in relation to Q-angle.

**Time Frame:** At baseline

### **Outcome Variables**

- Peak pressure (kPa)
- Contact area (cm^2)
- Contact time (ms)
- Maximum force (N)
- Maximum force normalized to body weight (%BW)

### **Plantar Regions**

- Toes
- Forefoot
- Midfoot
- Hindfoot
- Total foot

## **Study Procedures**

### **Q-Angle Assessment**

Bilateral Q-angle measurements are obtained under standardized conditions with participants in the supine position, knees extended, and quadriceps relaxed. Each extremity is measured three times using a standard goniometer, and the mean of the three trials is used for analysis. All measurements are performed by the same examiner.

### **Dominance Determination**

Lower-extremity dominance is determined according to the participant's self-reported preferred leg for kicking a ball.

## Dynamic Pedobarographic Assessment

Dynamic plantar pressure measurements are collected using an **Emed®-a50/D** pedobarography system (Novel GmbH, Munich, Germany). Participants walk barefoot at a self-selected comfortable speed along a 4-meter walkway with the pressure platform embedded flush with the floor. A mid-gait protocol is used. Familiarization trials are completed before formal data collection. At least three valid trials are recorded for each foot, and the mean of three valid trials is used in analysis.

## Statistical Analysis Plan

Descriptive statistics are reported as mean  $\pm$  standard deviation for continuous variables and frequency (n) and percentage (%) for categorical variables. Intra-rater reliability of repeated Q-angle measurements is evaluated using the intraclass correlation coefficient (ICC) with 95% confidence intervals. Standard error of measurement (SEM) and minimal detectable change at the 95% confidence level (MDC95) are also calculated.

Because bilateral extremity data are obtained from the same participant, observations are not considered independent. Therefore, linear mixed-effects models are used to account for within-subject correlation, with participant included as a random intercept. Q-angle is entered as a fixed effect in the main models. Separate models are fitted for each pedobarographic outcome and plantar region. Additional interaction analyses are conducted for sex and extremity dominance. To control for multiple comparisons, p-values are adjusted using the false discovery rate (FDR) method. Statistical significance is defined as a two-sided p-value of less than 0.05.

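### One Q-angle coefficient per random-intercept model blends the between-person and side-to-side associations; where these differ, the blend changes with the outcome, and the plan does not check whether they agree

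*Protocol*

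**What the plan says.** Under Q-Angle Assessment, both limbs are measured: "Each extremity is measured three times using a standard goniometer, and the mean of the three trials is used for analysis". Each participant therefore contributes two Q-angle values, which may differ.

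In the Statistical Analysis Plan section, "linear mixed-effects models are used to account for within-subject correlation, with participant included as a random intercept". The exposure is specified in one sentence: "Q-angle is entered as a fixed effect in the main models". Then "Separate models are fitted for each pedobarographic outcome and plantar region". The Outcome Variables section lists five variables and the Plantar Regions section lists five regions ("including the toes, forefoot, midfoot, hindfoot, and total foot" in the Detailed Description), which gives 5 × 5 = 25 main models. Sex and limb dominance appear only in additional interaction analyses. No other covariate is named for the main models.

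The Detailed Description states the aim: "The primary objective is to determine whether Q-angle is associated with selected regional plantar loading variables". It does not say whether that association is between people with different Q-angles or between the two limbs of one person. No person-mean term, centring or test of equal slopes is mentioned. Study Design gives "92 participants" as actual enrolment, with no sample-size calculation.

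**The concern.** With two limbs per person, two different questions can be asked. Do people with larger Q-angles load their feet differently from people with smaller ones? Within one person, is the limb with the larger Q-angle loaded differently from the other? A single Q-angle term assumes one answer to both, and it assumes that the random intercept is unrelated to Q-angle.

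Equal slopes are doubtful here. Sex, body size and walking pace differ between people. Maximum force is recorded in newtons as well as relative to body weight, contact area can depend on body size, and participants choose their own pace, which can affect contact time and pressure. If any of these relates to Q-angle, it shifts the between-person slope. As additive person-level effects, they cancel in the side-to-side contrast. The main models name none of them.

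What is at stake is interpretation. If the slopes differ, one outcome may show an association and another may not because their models weight the two slopes differently, even when the underlying slopes are the same in both.

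**Working it through.** **Inputs from the protocol.** 92 participants, two limbs each, so 184 limb observations; 25 main models; a participant random intercept; one Q-angle term. The protocol gives no slope, power or correlation figure to reproduce.

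**Assumed, because the protocol gives neither.** rx is the left-right correlation of Q-angle. ry is the left-right residual correlation of an outcome. rx is common to all models fitted to the same participants; ry is estimated separately in each model.

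**Formula.** Split each pair of limbs into a sum and a difference. The variance of Q-angle is proportional to 1 + rx in the sum and 1 − rx in the difference. The residual variance of the outcome is proportional to 1 + ry and 1 − ry. Weighting by information gives:

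- pooled slope = w × (side-to-side slope) + (1 − w) × (between-person slope)
- w = a/(a + b), with a = (1 − rx)/(1 − ry) and b = (1 + rx)/(1 + ry)

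**Worked values at rx = 0.8.** For ry = 0.5: a = 0.2/0.5 = 0.4, b = 1.8/1.5 = 1.2, w = 0.25. For ry = 0.95: a = 0.2/0.05 = 4, b = 1.8/1.95 = 0.923, w = 0.81.

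**Weight on the side-to-side slope over the assumed range:**

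| rx | ry = 0.3 | ry = 0.6 | ry = 0.9 | ry = 0.95 |
|---|---|---|---|---|
| 0.5 | 0.38 | 0.57 | 0.86 | 0.93 |
| 0.7 | 0.25 | 0.41 | 0.77 | 0.87 |
| 0.8 | 0.17 | 0.31 | 0.68 | 0.81 |
| 0.9 | 0.09 | 0.17 | 0.50 | 0.67 |

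The full range is 0.09 to 0.93. Within this one study rx is a single number, so the variation across the 25 models runs along one row.

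**Simulation check.** 92 participants × 2 limbs, 1000 replicates per scenario, maximum likelihood, rx = 0.7, standard-deviation units:

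| True between / within slope | ry | Pooled, formula | Pooled, simulated | Split model: between / within |
|---|---|---|---|---|
| 0.30 / 0 | 0.3 | 0.226 | 0.228 | 0.300 / 0.005 |
| 0.30 / 0 | 0.6 | 0.176 | 0.180 | 0.305 / 0.000 |
| 0.30 / 0 | 0.9 | 0.069 | 0.066 | 0.296 / −0.001 |
| 0.30 / 0.30 | 0.3 | 0.300 | 0.305 | 0.303 / 0.310 |
| 0.30 / 0.30 | 0.6 | 0.300 | 0.299 | 0.300 / 0.297 |
| 0.30 / 0.30 | 0.9 | 0.300 | 0.301 | 0.303 / 0.300 |

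With unequal slopes the planned coefficient moves with ry alone. With equal slopes it does not move.

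**Goniometer error alone.** Assume a single-reading error SD of 1.5 degrees, a side-to-side SD of 1.5 and a between-person SD of 3.5, with three readings averaged. The within slope is multiplied by 2.25/(2.25 + 0.75) = 0.75. The between slope is multiplied by (12.25 + 1.125)/(12.25 + 1.125 + 0.375) = 0.97. With equal true slopes of 1, the pooled slope is 0.25 × 0.75 + 0.75 × 0.97 = 0.92 at w = 0.25, and 0.81 × 0.75 + 0.19 × 0.97 = 0.79 at w = 0.81. The drop is about 13%.

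**Precision of the split model** (n = 92, rx = 0.8, standard-deviation units):

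- ry = 0.95: between SE = √[1.95/(92 × 1.8)] = 0.109; within SE = √[0.05/(92 × 0.2)] = 0.052; pooled SE = 1/√(84.9 + 368) = 0.047. Ratio of between to pooled: 2.3. SE of the difference: √(0.109² + 0.052²) = 0.12.
- ry = 0.5: between SE = √[1.5/(92 × 1.8)] = 0.095; within SE = √[0.5/(92 × 0.2)] = 0.165; pooled SE = 1/√(110.4 + 36.8) = 0.082. Ratio of within to pooled: 2.0. SE of the difference: 0.19.

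**The case against.** A random intercept is a standard and reasonable way to handle paired limbs, and nothing in the protocol shows that the two slopes differ. If they are equal, or both zero, the pooled slope is the better estimate because it is more precise. That stands, and it makes the point conditional.

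Four stronger readings are tempting, and the protocol does not support them:

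- **That the 25 slopes necessarily estimate different things.** This holds only where the between-person and side-to-side slopes differ. A four-fold spread in the pooled slope (0.75 down to 0.19 at rx = 0.8) needs an assumed between slope of 1, a within slope of exactly 0, and ry running from 0.5 to 0.95. The protocol gives none of these.
- **That measurement error by itself distorts the results badly.** Under the assumptions above it moves the pooled slope by about 13%.
- **That a planned comparison of regions is invalid.** No formal test between regions is planned, and slopes in kPa, cm², ms, N and %BW were never comparable across outcomes. Only informal contrasts between significant and non-significant regions are affected.
- **That the side-to-side slope is free of confounding.** It removes additive person-level effects only. Limb-level factors remain, and the protocol itself names dominance.

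It can also be said that adjusting for sex, body size and walking pace would narrow the gap, and that a fuller analysis plan, not shown here, might centre Q-angle. Adjustment would help, but it does not test whether the slopes agree. The protocol's own analysis section names a single term, and nothing else in the document qualifies it.

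Replacing the pooled term outright would be hard to defend, since precision falls and enrolment is already actual. This is why the fix adds a model and keeps the planned one.

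**Conclusion.** The point holds in conditional form. The protocol specifies one Q-angle term per random-intercept model for an exposure that varies at two levels. It does not say which association is meant, and it does not check that the two agree. Where they differ, the coefficient is a blend whose weight is set by the limb symmetry of each outcome and not by the research question. The weight on the side-to-side slope could lie anywhere from about 0.09 to 0.93 under the assumed correlations. The actual effect on this study's results cannot be computed, because neither limb correlation nor either slope is given. The random intercept itself is sound, and the pooled slope can be read as a common association wherever the two component slopes agree.

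**What to change.** For every outcome and region, keep the planned model and also fit one with two Q-angle terms: the participant's mean over both limbs, and the limb's deviation from that mean, with dominance as a covariate. Then:

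- Report both slopes with 95% confidence intervals, and their difference with its interval, beside the pooled slope.
- State which set of slopes the false discovery rate adjustment covers.
- Read the pooled slope as a common association only where the two slopes agree.
- Describe the within-person slope as free of additive person-level confounding, not as free of confounding.
- Label the analysis by when it was added, because enrolment is actual.

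The data are already collected. The cost is one extra Q-angle term per model, plus the dominance covariate, and intervals wider than the pooled one (up to about 2.3 times for the between slope at rx = 0.8 and ry = 0.95). Power to detect a difference between the slopes is limited: at rx = 0.8 its standard error is about 0.19 at ry = 0.5 and 0.12 at ry = 0.95. A non-significant difference should therefore not be taken as proof that the slopes are equal.

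### The main models name no adjustment covariate, so the primary Q-angle slope cannot be separated from differences in sex or body weight

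*Protocol*

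**What the plan says.** The Detailed Description sets the aim: "The primary objective is to determine whether Q-angle is associated with selected regional plantar loading variables". The Statistical Analysis Plan section then fixes the model. It is a linear mixed-effects model "with participant included as a random intercept", and "Q-angle is entered as a fixed effect in the main models". On scope: "Separate models are fitted for each pedobarographic outcome and plantar region". With five outcome variables and five regions, that is 5 × 5 = 25 main models.

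No adjustment covariate is named anywhere in the protocol. Sex and limb dominance enter elsewhere: "Additional interaction analyses are conducted for sex and extremity dominance". The Detailed Description makes these analyses secondary and directs them at effect modification: "Secondary analyses will explore whether these associations differ according to sex and limb dominance".

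Body weight appears once, under Outcome Variables, where maximum force is listed in newtons and again in scaled form ("Maximum force normalized to body weight (%BW"). Peak pressure, contact area, contact time and force in newtons carry no scaling.

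**The concern.** Sex may shift both Q-angle and plantar loading, and the plan itself treats sex as important enough to test as a modifier. Body weight bears on force, and the plan acknowledges this by listing a weight-scaled version of one variable. Yet the model behind the primary objective contains neither as a main effect.

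If men and women differ in Q-angle and also in, say, force in newtons, the Q-angle slope will be non-zero even when alignment has no relation to loading within either sex. The Detailed Description presents the study as being about alignment and loading patterns, so a reader will take a significant slope as a statement about alignment.

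Two features of the plan might seem to protect against this, but do not. The random intercept models the dependence between a person's two limbs; it does not adjust for characteristics of the person. The false discovery rate adjustment deals with the number of tests, not with slopes that are non-zero for another reason.

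**Working it through.** The protocol gives no sample-size, power or effect-size figure on this point, so there is nothing of its own to reproduce. The check therefore asks how far a sex difference alone can move the planned slope.

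**Inputs from the protocol:** "92 participants", two limbs each; random participant intercept; Q-angle as the only named fixed effect; two-sided 0.05.

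**Inputs assumed (none are in the protocol):** half of each sex; no Q-angle effect within sex; sex difference Δq in Q-angle of 0.5 or 1.0 within-sex SD; sex difference Δy in the outcome of 0.5, 1.0 or 1.5 SD, in the opposite direction; between-limb correlations (Q-angle, outcome) of (0.8, 0.6), (0.8, 0.8) and (0.6, 0.8).

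**Step 1: why the random intercept softens the bias but does not remove it.** For each person take s = (left + right)/√2 and d = (left − right)/√2. The mixed-model slope is approximately

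b = (C_s/λ + C_d) / (V_s/λ + V_d),

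where C and V are the covariance of Q-angle with the outcome and the variance of Q-angle, and λ is the ratio of the outcome's residual variance in s to that in d. Sex cancels out of d, so C_d = 0. In s, with half of each sex:

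- C_s = −0.5·Δq·Δy
- V_s = (1 + r_q) + 0.5·Δq²
- V_d = 1 − r_q
- λ ≈ [(1 + r_y) + 0.5·Δy²]/(1 − r_y)

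Example with Δq = Δy = 1, r_q = 0.8, r_y = 0.6:

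- C_s = −0.5; V_s = 1.8 + 0.5 = 2.3; V_d = 0.2; λ ≈ 2.1/0.4 = 5.25
- b ≈ (−0.5/5.25)/(2.3/5.25 + 0.2) = −0.0952/0.6381 = −0.149 SD per SD
- Between-person information alone would give −0.5/2.3 = −0.217

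The left-right contrast pulls the slope towards zero, but most of the bias remains. The simulated value for this setting is −0.154.

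**Step 2: simulation.** REML random-intercept fits, 1,000 runs per setting. Each row gives the range over the three correlation pairs.

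| Δq (SD) | Δy (SD) | p<0.05, Q-angle only | p<0.05, with sex | Bias, Q-angle only (SD per SD) |
|---|---|---|---|---|
| 0.5 | 0.5 | 6.7% to 9.4% | 5.6% to 6.1% | −0.018 to −0.043 |
| 0.5 | 1.0 | 10.8% to 15.4% | 5.0% to 5.6% | −0.041 to −0.083 |
| 0.5 | 1.5 | 13.3% to 25.9% | 5.3% to 5.4% | −0.050 to −0.123 |
| 1.0 | 0.5 | 12.0% to 16.7% | 4.8% to 5.4% | −0.044 to −0.073 |
| 1.0 | 1.0 | 25.8% to 47.6% | 4.9% to 5.3% | −0.077 to −0.154 |
| 1.0 | 1.5 | 38.3% to 67.8% | 5.0% to 6.4% | −0.101 to −0.215 |

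With sex in the model the bias is at most 0.007 in absolute value.

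**Step 3: the same question in degrees.** Assumed within-sex Q-angle SD is 3.5 degrees between people and 1.5 degrees between sides, with a sex difference of 2 to 4 degrees, an outcome difference of 0.5 to 1.5 SD and an outcome limb correlation of 0.6 to 0.9. Over 27 scenarios of 800 runs, rejection was 5.0% to 72.5% with Q-angle alone and 3.5% to 6.5% with sex added. A separate simulation on these assumed inputs gave about 8% to 75% and about 4% to 7%.

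**Limits.** All rates are per model at p<0.05, before the planned false discovery rate adjustment. Only sex was simulated. Body weight and limb dominance were not.

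**The case against.** The strongest reply is that the protocol asks about association and makes no causal claim. An unadjusted slope answers that question, and if it is non-zero because the sexes differ, rejecting is not an error about the marginal association. This stands. A reader might infer from the table that the primary test is invalid or has a false positive rate of up to 75%. The documents do not support that: the table takes the within-sex slope as its target, which the protocol never states, and it does not apply the planned multiplicity adjustment. What remains is a problem of interpretation.

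Second, the text calls Q-angle a fixed effect, not the only one, and a separate analysis plan could name covariates. A reader should therefore not say that covariates are ruled out. But the protocol's own analysis section sets out the random effect, the exposure, the model per outcome and region, and the interactions, and names no covariate. This is a model that has been specified, not a detail left open.

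Third, part of the problem is already addressed. Force is also analysed per body weight, and sex interaction models would ordinarily carry a sex main effect and show sex-specific slopes. True, but the scaling covers one variable of five, and the interaction models are secondary and answer a different question.

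Fourth, it is tempting to say that body size is already recorded. Only body weight is implied, through the scaled force. Stature and foot size appear nowhere. Weight also confounds only if it relates to Q-angle, which the documents neither show nor exclude. Likewise, dominance biases the slope only if Q-angle and loading both differ systematically by side, and nothing in the protocol quantifies that.

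**Conclusion.** The point holds as a weakness of interpretation. As written, the main models give a valid description of the unadjusted association, but cannot attribute it to alignment rather than to sex or body weight.

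The size cannot be derived from the protocol. Under the assumed inputs, a Q-angle effect that is null within sex is rejected at unadjusted p<0.05 in roughly 5% to 75% of runs, against about 5% with sex in the model. The low end means almost no harm and the high end serious harm. Where this study falls depends on its own sex ratio, sex differences and limb correlations. The weight component rests on reasoning alone.

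Severity: should-fix, as a cheap improvement with data that the plan already implies are held.

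**What to change.** In the Statistical Analysis Plan section:

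- Add sex as a fixed effect in all 25 main models.
- Add body weight in the models whose outcome is not already scaled to it. These are peak pressure, contact area, contact time and force in newtons, so 4 × 5 = 20 models.
- Base any statement about alignment on this adjusted model, and report the Q-angle-only model beside it as the unadjusted association.
- Limb dominance may be added as a fixed effect, on the understanding that its bias is unquantified.
- Do not call for stature or foot size, which the protocol does not record. Regional area as a percentage of total-foot area is not a general substitute, because it is constant at 100% for the total foot.
- Date and disclose the change. Enrolment is listed as actual, so data may already have been seen.

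The cost is wording, about two degrees of freedom with 92 participants, and possibly smaller slopes. No new measurement is needed: sex is required for the planned interactions and body weight for the scaled force.
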